## **5.4 DRUG CONCENTRATION MEASUREMENTS AND PHARMACOKINETICS**

Not applicable.

## **5.5 ASSESSMENT OF BIOMARKERS**

### **5.5.1 Biomarkers at screening**

N-terminal-pro Brain Natriuretic Peptide (NT-proBNP) will be measured at Visit 1 (screening) by the central laboratory and used to assess patient eligibility.

[figure not shown]
[REDACTED]

[REDACTED]

[REDACTED]

[REDACTED]

[REDACTED]

## 5.7 APPROPRIATENESS OF MEASUREMENTS

The majority of methods used in this trial, including ECHO, CPET and CMR, are considered standard in heart failure patients.

The following methods are not standard in heart failure patients:

### **Cardiac CT**

CT is the standard non-invasive procedure for the diagnosis of coronary artery disease. It is required in this trial in order to document any coronary artery disease.

### **Cardiac P Magnetic Resonance Spectroscopy (MRS)**

Myocardial phosphocreatine to adenosine triphosphate concentration ratio (PCr/ATP) is a sensitive indicator of the myocardial energy status, and phosphorus magnetic resonance spectroscopy (31P-MRS) allows noninvasive assessment of the PCr/ATP [[R17-0687](#), [R17-0691](#), [R17-0693](#), [R17-0695](#), [R17-0696](#), [R17-0697](#)].

### **Cardiac H MRS**

Proton (1H) magnetic resonance spectroscopy (MRS) allows non-invasive measurement of myocardial lipid (triglyceride) content, and by using this technique, elevated myocardial lipid (steatosis) has been shown in aortic stenosis, metabolic syndrome, obesity and type 2 diabetes mellitus, [R17-0688](#), [R17-0689](#), [R17-0690](#), [R17-0692](#), [R17-0694](#).

## 6. INVESTIGATIONAL PLAN

### 6.1 VISIT SCHEDULE

All patients are to adhere to the visit schedule as specified in the [Flowchart](#). If any visit has to be rescheduled, subsequent visits should follow the original visit date schedule calculated from the date of randomisation. The trial medication packs contain sufficient medication to allow for these time windows.

### 6.2 DETAILS OF TRIAL PROCEDURES AT SELECTED VISITS

Please refer to the Flowchart and [Section 5](#) for details of the procedures performed at each visit.

#### 6.2.1 Screening period

Following informed consent, the patient will undergo visit 1/screening assessments as indicated in the Flowchart. The assessments must all fall within the acceptable screening visit window but do not need to be performed on the same day. The patient should be registered in IRT as a screened patient.

There is no mandatory order of assessments but it is recommended that ECHO is performed prior to cardiac CT so that patients who are ineligible based on the ECHO are not required to undergo further assessment.

If the patient does not meet the eligibility criteria, the patient should be registered as a screen failure in IRT.

Re-screening is not allowed in this trial. Screening assessments may be repeated as long as they fall within the screening visit window. If more than one screening assessment is available, the latest assessment prior to randomisation must be used to assess eligibility.

If the patient meets the eligibility criteria during screening (Visit 1), Visit 2 should be scheduled. Any baseline conditions which are present at Visit 1 should be reported in the eCRF.

#### 6.2.2 Treatment period

##### Visit 2 (Randomisation)

The investigator must perform a final assessment of eligibility when the results of all screening assessments are available. If the patient does not meet the eligibility criteria, the patient should be registered as a screen failure in IRT. Re-screening is not allowed in this trial.

If the patient is eligible for trial participation, the patient is randomised using IRT and treatment is allocated. The visit 2 assessments as listed in the [Flowchart](#) are then performed. Some assessments do not need to be repeated if performed during the last 7 days as part of the screening visit; see [Flowchart](#) for details.

The patient should be fasting in preparation for the blood sampling at this visit (no food or liquid except water for at least 6 hours prior to sampling). The following rules apply for the order of assessments at this visit;

- [REDACTED]
- Blood tests and iv cannulation must be performed before the CMR scan.
- Echo must be performed before Dobutamine stress
- CPET must be performed before Dobutamine stress
- All Visit 2 assessments must be performed before the first dose is taken

### Visit 3 (Day 15)

The patient will return to the clinic for visit 3 on day 15 ± 1 day of treatment. The purpose of this visit is to check patient safety, to check medication compliance and to perform limited assessments. Assessments to be performed are indicated in the Flowchart. [REDACTED]

### Visit 4 (Day 84)

Visit 4 will take place on Day 84 of treatment, which is also the last day of treatment. If the visit cannot be scheduled for Day 84, it should be scheduled as close as possible, but within 4 days and the patient should continue to take the medication daily until the day of the visit. All Visit 4 assessments must be performed within 48 hours of the last dose, regardless of which day this is. The patient should be asked to return all remaining medication during this visit.

The assessments to be performed at Visit 4 are indicated in the Flowchart. The patient should be fasting in preparation for the blood sampling at this visit (no food or liquid except water for at least 6 hours prior to sampling). The following rules apply for the order of assessments at this visit;

- [REDACTED]
- Blood tests and iv cannulation must be performed before the CMR scan.
- Echo must be performed before Dobutamine stress
- CPET must be performed before Dobutamine stress

### 6.2.3 Follow up period and trial completion

A follow up visit (Visit 5) will be performed 7-14 days after the last dose of trial medication. The expectation is that this visit will be performed via a telephone call, but where appropriate, a clinic visit may be scheduled. The assessments to be performed at Visit 5 are indicated in the [Flowchart](#).

Visit 5 marks the completion of the study for the individual patient. After the completion of the study the patient will receive standard medical care.

### 6.2.4 Early discontinuation of trial medication

See [Section 3.3.4.1](#) for procedures to be followed in case a randomised patient does not reach Visit 4 for any reason.

## 7. STATISTICAL METHODS AND DETERMINATION OF SAMPLE SIZE

### 7.1 STATISTICAL DESIGN MODEL

This is a randomised, double-blind, single-centre placebo-controlled trial. The eligible patients for this trial will be randomised to empagliflozin 10 mg or placebo in a 1:1 ratio. Randomisation will be stratified by cohort (HFpEF / HFrEF) and history of diabetes (Yes / No).

The primary endpoint of change from baseline in cardiac energetics (PCr/ATP ratio) at rest is regarded as normally distributed based on literature data.

Change from baseline of cardiac energetics (PCr/ATP ratio) at rest after 12 weeks of treatment will therefore be analyzed by an analysis of variance (ANOVA) model. The model will include treatment, presence of atrial fibrillation at baseline (Yes / No) and history of diabetes (Yes / No) as fixed effects.

The analysis will be performed on the per protocol set (PPS) of patients having a valid PCr/ATP ratio measurements available at baseline and at week 12, and not having an important protocol violation relevant to the primary endpoint.

All planned analyses will be conducted separately on the two cohorts.

### 7.2 NULL AND ALTERNATIVE HYPOTHESES

The null hypothesis is that for patients in HFrEF and HFpEF cohorts, the change from baseline to week 12 in the resting state PCr/ATP ratio measured by P MRS is not different from placebo. The alternative hypothesis is that the change is different.

If the null hypothesis is rejected, and the result is more favourable for empagliflozin, superiority is concluded in the tested cohort.

The primary objective will be addressed by a two-sided test at level  $\alpha=0.05$  conducted separately for each cohort.

### 7.3 PLANNED ANALYSES

Adherence to the protocol (such as inclusion/exclusion criteria, times of measurement, compliance with intake of trial medication, treatment dispensing errors, prohibited concomitant medication, completeness and consistency of data) will be checked. Important protocol violations (IPVs) will be identified no later than in the Blinded Report Planning Meeting and provided in the TSAP.

The following analysis sets will be defined for this trial:

- Randomised set (RS):  
This subject set includes all randomised patients, whether treated or not.
- Treated set (TS):

This patient set includes all subjects from the RS who were documented to have received one dose of study drug. This is the Intent to treat (ITT) population.

- Per-protocol set (PPS):  
This patient set includes all patients from the TS who provide evaluable data at baseline and on-treatment for the primary endpoint and are not affected by protocol violations relevant to the statistical evaluation of the primary endpoint.

Whether a primary endpoint data is evaluable or a protocol violation is relevant will be decided no later than at the final Blinded Report Planning Meeting (BRPM).

Relevant protocol violations may include:

- Use of prohibited medication
- Patient was non-compliant to study drug intake (e.g.: study drug compliance <80%)

For both efficacy and safety analyses, treatment will be evaluated as treated.

Baseline will be defined as the last available measurement before start of randomised trial medication.

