#### 3.3.4.1 Withdrawal from trial treatment

An individual patient is to be withdrawn from trial treatment if:

- The patient wants to withdraw from trial treatment, without the need to justify the decision.
- The patient does not want to undergo the trial assessments at visit 4 required to assess the primary endpoint.
- The patient needs to take concomitant drugs that interfere with the investigational product or other trial medication (see [Section 4.2.2](#)).
- The patient becomes pregnant. Note that the patient must be followed until the end of the pregnancy (see [Section 5.3.5.2](#)).
- The patient can no longer be treated with trial medication for other medical reasons (such as surgery, AEs or other diseases).
- The patient has repeatedly shown to be non-compliant with important trial procedures and/or, in the opinion of both the investigator and sponsor representative, is not willing or able to stick to the trial requirements in the future.

In the event that a patient is withdrawn from trial treatment prior to Visit 4, the patient should be asked to return all remaining trial medication. If the patient’s agrees, the following EOT safety assessments will be conducted;

- Pregnancy test
- Safety laboratory tests
- Vital signs

In addition, if the patient agrees, the patient will have a follow-up visit 7-14 days after the last dose of trial medication.

For all patients the reason for withdrawal from trial treatment (e.g. AEs) must be recorded in the eCRF. These data will be included in the trial database and reported.

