#### **4.1.4 Drug assignment and administration of doses for each patient**

Trial medication will be assigned via IRT at randomisation and dispensed in a double-blind manner. At Visit 2 the patient will be dispensed sufficient medication for the whole treatment period. Further dispensing will only occur in the event that the patient requires replacement medication. For further details regarding packaging please refer to [Section 4.1.6](#).

From the start of the treatment period patients will be instructed to take the trial medication once daily with a glass of water. Empagliflozin can be taken with or without food.

To ensure a dose interval of about 24 hours, the medication should be taken at approximately the same time every day, preferably in the morning. If a dose is missed by more than 12 hours, that dose should be skipped and the next dose should be taken as scheduled. No double doses should be taken. On the day of Visit 4 the dose should be taken at the usual scheduled time, regardless of the timing of assessments.

For logistical reasons, Visit 4 can be scheduled on Day 84 ± 4 days. Daily dosing should continue until the day of Visit 4, when the last dose is taken. Sufficient extra medication is provided in case Visit 4 takes place later than Day 84.

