### 7.3.1 Primary endpoint analyses

The patient set for the evaluation of cardiac energetics endpoints will be the PPS.

Change from baseline of cardiac energetics (PCr/ATP ratio) at rest after 12 weeks of treatment will be analyzed by an analysis of variance (ANOVA) model. The model will include treatment, history of atrial fibrillation and history of diabetes as fixed effects.

A sensitivity analysis will be conducted on the randomized set (ITT population). Subgroup analyses will be performed for the primary endpoint including subgroup analyses by history of diabetes and by eGFR (CKD-EPI)Cr at baseline (<60 vs ≥60 mL/min/1.73m^2).

For the subgroup analysis an ANOVA model as the primary will be conducted, additionally including the terms of the subgroup and subgroup by treatment interaction.

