2.1.3 Handling of Outliers and Missing Data

For the primary outcome, patients who do not have a measurement taken at baseline and week 12 will be excluded from the primary analysis. For primary analyses, missing efficacy data will not be imputed.

Any outliers will be identified and documented prior to the database lock and unblinding. Cases that are visually “extreme” will be assessed for possible influence on the results and conclusions by comparing results from analyses with or without outliers. Any discrepant results from the two analyses will be reported and discussed in the CTR and publication manuscripts.

[figure not shown]

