3.2 Randomised Set (RS)

This set will include all subjects who are randomised to study treatment. The RS set will be employed for a sensitivity analysis to check for an unbiased estimation of the primary endpoint result if a substantial number of protocol violations resulted in a reduced sample size used for the primary endpoint estimates. The analysis of exploratory endpoints will be performed on the RS of patients with available data.

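### Protocol 7.3 evaluates efficacy by treatment received, which contradicts the randomised-set ITT sensitivity analysis in 7.3.1; ITT names two sets, and SAP 3.2 leaves unclear whether that analysis is always run

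*Protocol*

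**What the plan says.** Three statements in the protocol bear on this.

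- Section 7.3, grouping rule: "For both efficacy and safety analyses, treatment will be evaluated as treated". No analysis is exempted.
- Section 7.3, on the treated set (patients with a documented dose): "This is the Intent to treat (ITT) population".
- Section 7.3.1: "A sensitivity analysis will be conducted on the randomized set (ITT population". Section 7.3 defines the randomised set as all randomised patients, dosed or not.

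The primary analysis in 7.3.1 uses the per-protocol set (PPS). The items that 7.3 lists for checking include "treatment dispensing errors, prohibited concomitant medication, completeness and consistency of data", so wrong-arm dispensing is foreseen.

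The visible SAP adds the following.

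- Section 3.3 groups safety summaries by actual treatment. Section 5.3.1 names the treatment factor without saying randomised or received.
- Section 1.4 keeps the main analysis as in the protocol. It lists two changes, both about adding baseline as a covariate.
- Section 3.2 says the randomised set will be used for a sensitivity analysis "if a substantial number of protocol violations resulted in a reduced sample size used for the primary endpoint estimates". No number is given.
- Appendix 2, code C1.02, covers wrong-arm medication for more than 20% of treatment. Its exclusion column says None, on a list described as tentative.

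**The concern.** The sensitivity analysis in 7.3.1 is the plan's only visible analysis of the primary endpoint on a set not selected by protocol adherence. Under the 7.3 rule it would be grouped by drug taken, so it would not be the analysis its label promises. The rule also cannot classify a randomised patient who never took a dose. Nor does any visible rule say where a patient who took both drugs belongs.

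With about 15 evaluable patients per arm, moving one patient between groups can change whether a result is significant. SAP Appendix 2 says that C1.02 can be finally judged only after database lock, because it needs unblinding information. A grouping rule left open until then would be settled with treatment known.

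The double use of ITT and the if-clause in SAP 3.2 add to this. A reader cannot tell from the visible text which set is meant, or whether the analysis will certainly be run.

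**Working it through.** **1. The plan's own figure.** Protocol 7.7 gives an effect of 0.3, SD 0.28, two-sided alpha 0.05 and 80% power, hence 30 evaluable and 43 randomised per cohort. The noncentral-t power of a two-sample test with 15 per arm is 80.8%, and with 14 per arm 77.9%, so 30 is reproduced. With drop-out, 30/0.7 = 42.9, rounded up to 43. This point does not dispute these figures.

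**2. The texts side by side.**

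| Question | Protocol 7.3 | Protocol 7.3.1 | Visible SAP |
|---|---|---|---|
| Efficacy grouping | As received, no exception | ITT label implies as randomised | Not stated; 1.4 keeps the protocol's main analysis |
| Set called ITT | Treated set | Randomised set | Not stated |
| Is the randomised-set analysis run? | – | Yes | Yes, with an if-clause (3.2) |

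**3. What the ITT label changes.** Very little. The two sets differ only by undosed patients. They would ordinarily have no week-12 scan, and for the primary analysis SAP 2.1.3 says "patients who do not have a measurement taken at baseline and week 12 will be excluded from the primary analysis", with no imputation.

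**4. What the grouping rule changes.** Assume that m of 15 placebo patients took empagliflozin throughout and that the errors are unrelated to outcome. The documents give no such counts. A whole-course error is the natural case, because "At Visit 2 the patient will be dispensed sufficient medication for the whole treatment period". The expected difference as randomised is 0.3 × (15 − m)/15: 0.3 × 14/15 = 0.28 for m = 1 and 0.3 × 13/15 = 0.26 for m = 2. As treated it stays at 0.30. Simulation (200,000 runs, two-sample t-test, SD 0.28, true effect 0.3) gives:

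| m | Power as randomised | Power as treated | Verdicts differ | Only as treated significant | Only as randomised significant |
|---|---|---|---|---|---|
| 0 | 0.81 | 0.81 | 0% | 0% | 0% |
| 1 | 0.74 | 0.81 | 11% | about 9% | about 2% |
| 2 | 0.67 | 0.80 | 19% | about 16% | about 2.5% |

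At no true effect the verdicts differ in about 3% (m = 1) and 5% (m = 2) of trials, and both tests keep the 5% level.

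**5. Mixed exposure.** The C1.02 threshold is 0.20 × 84 = 16.8 days, so 17 or more days on the wrong drug is flagged. The visible text does not say at what point such a patient changes group.

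**6. What the randomised-set run can recover.** Per cohort, 43 − 30 = 13 patients are expected to drop out. After early withdrawal, protocol 3.3.4.1 says that, if the patient agrees, "the following EOT safety assessments will be conducted"; the list is a pregnancy test, safety laboratory tests and vital signs, without cardiac magnetic resonance (CMR). Restricted medication requires permanent discontinuation (4.2.2), which leads to the same list. Compliance below 80% permits limited Visit 4 assessments (4.3). The patients who can be added back are therefore mainly those excluded for eligibility, for a missing stress scan (code E1.06) or case by case.

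If 2, 4 or 6 patients were added to 30 (assumed, exclusion at random), the chance at no effect that the PPS is significant and the randomised set is not is 1.2%, 1.6% or 1.9%. The reverse is equally likely. This is sampling noise and does not measure selection bias.

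**The case against.** The best defence is that as-treated grouping in a per-protocol, mechanistic analysis is a prespecified choice. The table in step 4 supports it: when errors are random, as-treated grouping keeps the estimate at 0.30, the level at 5% and the power near 0.81. Most of the 11% and 19% disagreement consists of true effects that only as-treated grouping detects. The PPS is in any case a subset selected after randomisation. All of this stands. A reader might infer that the rule invalidates the primary analysis or inflates its error rate, and the documents do not support that.

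A reader might also infer from C1.02 that wrong-arm patients certainly stay in the PPS. That is not settled. SAP 3.1 calls the list suggestive and subject to change, and Appendix 2 calls it tentative. Its entries are not a safe guide either: code C3.01 (non-compliance) also shows None, whereas protocol 4.3 says a patient below 80% compliance at Visit 4 will not be used in the primary analysis.

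On SAP 3.2, a reader might infer that the sensitivity analysis has been made conditional. The clause may only describe its purpose, which fits the unconditional protocol text and the absence of a listed change. SAP 1.4 also announces a sensitivity analysis with baseline as covariate that no visible section specifies, and the contents list has a redacted entry between 5.3.1 and 5.4. Relevant text is probably hidden there.

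Finally, allocation by interactive response technology (IRT) and a single dispensing make wrong-arm errors unlikely. That limits the size of the problem but does not remove the contradiction.

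**Conclusion.** The contradiction between 7.3 and 7.3.1 is real and should be corrected: a blanket as-treated rule defeats an analysis that the plan promises under an ITT label. No visible SAP text repairs it. The double use of ITT is a labelling fault with almost no numerical effect. Whether SAP 3.2 sets a condition remains uncertain.

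The size is small. The grouping conflict changes no result if nobody takes wrong-arm medication. The shifts to 0.28 and 0.26 rest on assumed counts, whole-course errors and errors unrelated to outcome. The superiority decision rests on the PPS, so the randomised-set run is supporting evidence, and it recovers few of the patients lost. For the PPS primary analysis, the point is only that the grouping should be a deliberate, stated choice made before unblinding.

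**What to change.** In protocol 7.3, or in SAP 1.4 and 3.2 if the protocol is not amended:

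- State that the randomised-set sensitivity analysis groups patients as randomised, and that safety analyses group them by treatment received.
- State before unblinding which grouping the PPS primary analysis uses. As randomised is the conventional default for efficacy. If as treated is kept, add a rule for patients who took both drugs.
- Use ITT for one set only.
- Delete the if-clause in SAP 3.2, so that the primary model is always also run on randomised patients with resting PCr/ATP at baseline and week 12. Label it as an available-data analysis and not as full ITT.

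The cost is a few sentences and at most one further model run per cohort, with no new data. If the PPS is grouped as randomised and wrong-arm errors occur, power falls to about 0.74 with one such patient of 15 and 0.67 with two, against 0.81 with none. Without errors nothing is lost.

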### 7.3.1 Primary endpoint analyses

The patient set for the evaluation of cardiac energetics endpoints will be the PPS.

Change from baseline of cardiac energetics (PCr/ATP ratio) at rest after 12 weeks of treatment will be analyzed by an analysis of variance (ANOVA) model. The model will include treatment, history of atrial fibrillation and history of diabetes as fixed effects.

A sensitivity analysis will be conducted on the randomized set (ITT population). Subgroup analyses will be performed for the primary endpoint including subgroup analyses by history of diabetes and by eGFR (CKD-EPI)Cr at baseline (<60 vs ≥60 mL/min/1.73m^2).

For the subgroup analysis an ANOVA model as the primary will be conducted, additionally including the terms of the subgroup and subgroup by treatment interaction.

